8.3 Demographic and Baseline Characteristics

The following summaries will be provided for the Safety Analysis Set and for the PK Analysis Set if the PK Analysis Set differs (see [Sections 5.3](#) and [5.5](#)):

- Demographic characteristics: sex, race, ethnicity, age, height at Screening, body weight and body mass index (BMI) at Baseline.
- HAE history: history of laryngeal attack (yes, no), family history of HAE (yes, no), age at diagnosis of HAE, HAE type (C1-INH type 1, C1-INH type 2), number of HAE attacks during 6 months before Screening or before the start of prophylactic therapy, prophylactic HAE therapy within 6 months before Screening (yes, no), primary locations of HAE attacks in the last 6 months prior to Screening (up to 3 may be selected).
- Medical history by system organ class (SOC) and preferred term (PT) – include medical history with an end date prior to informed consent date.
- Concomitant diseases by SOC and PT – include medical history with an end date after informed consent or flagged as ongoing.

Medical history and concomitant diseases will be coded by Medical Dictionary for Regulatory Activities (MedDRA). There will be periodic updates of the MedDRA version. The latest licensed version will be used and indicated in the final analysis, and version updates will be implemented upon availability.

By-subject listings for all available data using the Enrolled Analysis Set (see [Section 5.2](#)) will be provided for each category mentioned above and further for:

- Reproductive system findings (childbearing potential, method of birth control, date and time of pregnancy test, specimen type, and pregnancy test result) – applicable to children above 5 years of age.

Those listings will contain a Safety and PK flag.

8.4 Prior/Concomitant Medications

Reported medications will be coded using World Health Organization (WHO) Drug Global Dictionary. There will be periodic updates of the WHO Drug Global Dictionary version. The latest licensed version will be used and indicated in the final analysis, and version updates will be implemented upon availability. The summary of medications will show the number and percentage of subjects taking medication displayed for Anatomical Therapeutic Chemical

(ATC) class level 4 and PT. If the level 4 ATC name is not available, then the available next lower level will be used.

The reported medication will be classified as "Prior only", "Prior and concomitant" or "Concomitant only". These 3 categories are mutually exclusive:

- "Prior only": if the subject has not taken any IP; or if the medication end date [/time] is before IP start date [/time]. If the medication end date is partially missing, the medication will only be assigned to 'Prior only' if the partial date gives clear evidence that the medication stopped before IP start date.
- "Concomitant only": if the medication start date [/time] is on or after IP start date [/time]. If the medication start date is partially missing, the medication will only be assigned to 'Concomitant only' if the partial date gives clear evidence that the medication started on or after IP start date.
- "Prior and concomitant": if the medication start date [/time] is before IP start date [/time] and the medication end date [/time] is on or after IP start date [/time]. If the medication start date or end date are partially or completely missing, the medication will be assigned to 'Prior and concomitant' unless there is clear evidence that the medication stopped before IP start date (that is, the medication should be assigned to "Prior only") or that the medication started after IP start date [/time] (that is, the medication should be assigned to "Concomitant only").

Summary tables will be provided for "Prior and concomitant" and "Concomitant only" medications. In the summary of prior and concomitant medications, each subject will be counted once within each unique term.

On-demand HAE medication will be summarized besides the WHO Drug ATC classes as a separate block (as a "virtual" ATC class "On-demand HAE Medication") within the summaries of prior and concomitant medication including:

- On-demand HAE medications prior to the Treatment Period collected in the eCRF 'Concomitant and Prior Medications' with Primary Indication as "Study Indication (Acute HAE Treatment)".
- On-demand HAE medications on/after start of the Treatment Period collected in a separate eCRF 'On-demand Treatment'.

The on-demand HAE medication will also be reported in their original ATC class.

Summaries and by-subject listings will be provided based on the Safety Analysis Set (see [Section 5.3](#)). Listings will include medication/therapy start and end date/time or ongoing status, dose, route, frequency, primary indication for the medication, AE term if applicable, medical history term if applicable and concomitant medication flag (Prior, Prior / Concomitant, Concomitant).

8.5 Study Population - Derived Variables

Derivation of BMI at Baseline

BMI will be calculated using the following formula:

$$\text{BMI (kg/m}^2\text{)} = \text{Weight (kg)} / [\text{Height (m)}]^2$$

using the height measured at Screening and the weight measured at Baseline (see [Section 7.2.3](#)). If weight at Baseline is not available, the BMI will be missing.

BMI at later visits will be derived based on the most recent assessment of height and weight at the respective visit.

9 Efficacy Analyses

The primary objective of the study is to evaluate the safety and PK of SC administration of CSL312 in the prophylactic treatment of pediatric subjects with C1-INH HAE. Thus, the primary endpoints of the study are a safety and PK endpoint and not an efficacy endpoint. Please see [Section 10.2.1](#) and [Section 11](#) for a description of the primary safety and PK endpoints, respectively, and corresponding analysis.

Subjects who turn 6 years of age during the study will remain on their dosing regimen from study start and will be analyzed in the age group according to the subject's age at the time of consent.

The efficacy endpoints will not be included in any efficacy summary if the subject's duration for the Treatment Period is less than 30 days, i.e., the subject discontinued within 30 days after the Day 1 Visit date or the date of first IP, if available. The reason why an endpoint is not included will be provided in the by-subject listing.

The efficacy endpoints will also be assessed over time for 6-months' time windows, with the first window starting at the Day 1 Visit date or the date of first IP, if available. Only subjects who completed the entire time window (i.e., completed Visit Month 6 and Visit Month 12,

respectively) – allowing for visit windows as per Schedule of Assessment in the protocol – will be included in the analysis of this time window.

9.1 Analysis of Primary Endpoint

The primary endpoint of the study is not an efficacy variable.

9.2 Analysis of Secondary Endpoints

The secondary efficacy endpoints are:

- Time-normalized number of HAE attacks.
- Time-normalized number of HAE attacks treated with on-demand treatment.
- Time-normalized number of moderate and / or severe HAE attacks.
- Time-normalized number of HAE attacks by severity (mild, moderate, severe).
- Percentage reduction in the time-normalized number of HAE attacks.

9.2.1 Secondary Efficacy Analysis

The secondary efficacy endpoints will be analyzed using the Enrolled Analysis Set (see [Section 5.2](#)). The endpoint "time-normalized number of HAE attacks" will also be analyzed using the PP Analysis Set (see [Section 5.4](#)). This will also be applied to the supplementary analysis of secondary endpoints.

Subjects / caregivers will enter HAE symptoms into their electronic Diary and the start and end date and time, the interference of HAE symptom(s) with daily activities, and location(s) of the HAE symptom(s). Investigator-reported HAE attacks will be based upon review of subject diaries, relevant interval medical history, and physician judgment. The investigator may ask clarifying questions to assist in his / her assessment of whether an HAE attack occurred. If an attack occurred, the investigator would record the attack in the eCRF, the start / end date, the attack location(s), and the severity of the attack based on the most severe symptoms.

For all analyses considering HAE attacks, only the HAE attacks confirmed and reported by the investigator on the eCRF 'HAE Attacks' will be used.

HAE attacks with a start date and time after the first IP administration through the EoT Visit date (or last available visit or event date [whichever is later] if no EoT Visit date is available) will be counted for the Treatment Period and will be included in the analyses of efficacy. If the EoT Visit of a subject is delayed by more than the treatment time window relative to the

last IP administration, HAE attacks with a start date and time after first IP administration through the date and time of the last IP administration + 30 or 60 days for Q1M or Q2M regimen, respectively, will be counted for the Treatment Period. For subjects not treated, start date for counting the HAE attacks will be the Day 1 Visit date. HAE attacks without start time will be counted only if they start after Day 1 or the day after the date of first IP.

HAE attacks will be listed, including start date / time, end date / time, time between start of the attack and end of the most recent preceding attack or Day 1 Visit /first IP administration (if no preceding attack), anatomical locations, severity, most recent actual CSL312 dose and dosing date and time, potential trigger, duration in hours and days, period in which the HAE attack occurred and how many and which on-demand medications were taken per HAE attack.

The following derived endpoints based on HAE attacks will be presented together in a listing (overall, by 6-months' time window, and until Day 31 of the Treatment Period):

- Time-normalized number of HAE attacks (per month and per year).
- Time-normalized number of HAE attacks treated with on-demand treatment (per month and per year).
- Time-normalized number of moderate and / or severe HAE attacks (per month and per year).
- Time-normalized number of HAE attacks by severity - mild, moderate, severe (per month and per year).
- Length of the Treatment Period.
- Total number of HAE attacks.
- Time-normalized number of HAE attacks based on historical data.
- Reduction in attack rate (treatment period versus historical data).

9.2.1.1 Time-normalized Number of HAE Attacks

The time-normalized number of HAE attacks per subject will be calculated as defined in [Section 9.3](#).

The time-normalized number of HAE attacks per month and per year will be summarized descriptively including median (of primary interest) and mean (of secondary interest) with corresponding two-sided 95% confidence intervals (CIs). The CIs for the mean will be based on the t-distribution while distribution-free CIs will be calculated for the median.

The time-normalized number of HAE attacks will also be calculated for the historical data collected at Screening (number of HAE attacks 6 months prior to Screening or the start of prophylactic treatment). The length of the period (denominator) will be set to 6 months.

Besides the time-normalized number of HAE attacks, the total number of HAE attacks (i.e., not time-normalized) will also be summarized.

9.2.1.2 Time-normalized Number of HAE Attacks Treated with On-demand Treatment

An HAE attack treated with on-demand treatment is identified by the question "On demand treatment taken?" being answered with "Yes" on the eCRF 'HAE Attacks'. The time-normalized number of HAE attacks treated with on-demand treatment will be calculated as defined in [Section 9.3](#).

The monthly and yearly rates will be summarized descriptively.

This summary table will also include the number and percentage of subjects who took a specific medication at least once and the total number of times a specific on-demand medication was used across all subjects. For each on-demand medication, the number of uses of the on-demand medication per HAE attack will be summarized descriptively. ATC classification and PT will be included in the by-subject listing.

The analysis described above will be repeated including only moderate / severe HAE attacks as well as by attack severity (mild, moderate, severe).

9.2.1.3 Time-normalized Number of HAE Attacks by Attack Severity and for Moderate and/or Severe HAE Attacks

The analysis and derivation as described in [Section 9.2.1.1](#) will be repeated including only moderate and/or severe HAE attacks as well as by attack severity (mild, moderate, severe).

9.2.1.4 Percentage Reduction in the Time-normalized Number of HAE Attacks

The percentage reduction in the time-normalized number of HAE attacks will be calculated for each subject as defined in [Section 9.3](#).

The percentage reduction in the time-normalized number of HAE attacks will be summarized descriptively.

The number and percentage of responders and non-responders will be presented with 95% CIs. A subject is classified as a responder if the percentage reduction in the time-normalized number of HAE attacks under treatment compared to the historical data in the medical records is $\geq 50\%$. In addition, the number and percentage of subjects with percentage reductions of $\geq 70\%$ and $\geq 90\%$ will be presented with 95% CIs.

Furthermore, the number and percentage of subjects with a percentage reduction of 100%, i.e., who did not experience an HAE attack (attack-free) will be presented and summarized with 95% CIs.

The 95% CIs for percentages will be calculated based on Wilson's asymptotic confidence limits.

9.2.1.5 Supplementary Analysis of Secondary Endpoints

The endpoints listed in [Section 9.2](#) will be calculated for the entire Treatment Period and by 6-months' time window.

Time-normalized number of HAE attacks, the time-normalized number of HAE attacks treated with on-demand treatment, time-normalized number of HAE attacks by severity (mild, moderate, severe), and time-normalized number of moderate/severe HAE attacks will also be assessed for a time window starting from date of first IP (or Day 1 Visit date if the subject did not receive IP, see [Table 3](#)) until Day 31 of the Treatment Period. This summary will be provided by dosing regimen and overall. The number and percentage of subjects not experiencing any attacks in the first month (i.e., 31 days) will also be displayed.

Subjects who completed the first month (Day 31 of the Treatment Period) will be included in the analysis for this window.

Subjects' profiles will be generated for each subject. The x-axis will show the HAE historical data and the Treatment Period. The different subject IDs will be plotted on the y-axis. For each subject, a horizontal bar will show the duration of his / her study participation; dots at the respective position of the x-axis will symbolize a mild (white dot), moderate (gray dot), and severe (black dot) HAE attack; an arrow above the bar at a certain position of the x-axis will show the time point when the subject took on-demand medication during the Treatment Period (for historical data prior to Screening information about on-demand medication will be used if available), and an asterisk will show the time of CSL312 administration. In addition, the subject's reason for study discontinuation (if applicable) will be given. Subjects'

profiles will be sorted by dosing regimen, showing subjects receiving 100 mg Q2M, followed by the profiles of subjects receiving 100 mg Q1M.

Time to Event Analysis

The following events will be analyzed:

- Time to first HAE attack after Day 1 Visit date (if no start time for the attack available or for subjects not treated) or after the date and time of first IP. Subjects without attacks will be censored at the EoT Visit date (or last available visit or event date if no EoT Visit date is available).
- Time from end of first HAE attack to start of second HAE attack (only for subjects experiencing at least one attack which ends within the Treatment Period). Subjects without a second attack will be censored at the EoT Visit date (or last available visit or event date if no EoT Visit date is available).
- Time from end of second to start of third HAE attack (only for subjects experiencing a second attack which ends within the Treatment Period). Subjects without a third attack will be censored at the EoT Visit date (or last available visit or event date if no EoT Visit date is available).

The following will be derived and analyzed for all subjects in the Enrolled Analysis Set:

- Maximum attack-free time.

The maximum attack-free time is defined as the maximum time a subject was attack-free between all subsequent HAE attacks the subject experienced. The maximum attack-free time for subjects without attacks is equal to the length of the subject's efficacy evaluation period. For the derivation see [Section 9.3](#).

For derivation of the times-to-event see [Section 7.2.2](#). Time-to-events will be derived within the Treatment/Efficacy Evaluation Period (see [Table 2](#)).

For each of the events above the following will be presented:

- The number and percentage of subjects who do not experience the event (not applicable for the maximum attack-free time).
- The median time, the 75% and 25% percentile times of subjects being event-free / having no second / having no third HAE attack, respectively. The median, 25%, and 75% percentile times are defined as the times for which the Kaplan-Meier estimates for the time-to-event functions equal 0.5, 0.75, and 0.25, respectively.
If the time-to-event function is horizontal at 75%, 50% or 25%, the median or

percentiles will be calculated as the average of the two values between which the time-to-event function is horizontal.

- The minimum and maximum times to the event.

Kaplan-Meier curves with two-sided 95% CI will be plotted showing the percentage of subjects being event-free at certain times.

For time between first and second/time between second and third attack the percentages will be calculated using the number of subjects not having the second/third attack at that time as the numerator and the number of subjects having at least one/two event(s) as the denominator.

The corresponding life tables will also be presented.

A by-subject listing will be provided for

- Time to first attack (in days),
- Time between first and second attack and time between second and third attack, if applicable,
 - or Time until the EoT Visit (or last available visit or event date if no EoT Visit date is available) if no subsequent attack occurred.
- Maximum attack-free time (in days).

It will be indicated whether the observation is censored.

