The number of HAE attacks experienced by each subject, as well as the timing of (recurrent) HAE attacks, will be assessed. Different time-to-event analyses will be performed (eg, time to first HAE attack and maximum attack-free time). The maximum attack-free time is defined as the maximum time a subject was attack-free between all subsequent HAE attacks, calculated as start date / time of the following HAE attack - end date / time of the preceding HAE attack. Subjects with no HAE attack, no second HAE attack, no third HAE attack, etc, will be censored at the End of Treatment Visit. The maximum attack-free time for subjects with no attacks is equal to their length of treatment.

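### SAP 9.2.1.5 names Kaplan-Meier for the gaps to the second and third attack, then defines their percentages by a fraction that ignores censoring

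*SAP*

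**What the plan says.** The time-to-event part of SAP 9.2.1.5 covers the time to the first attack, the gap from the end of the first attack to the second, and the gap from the end of the second to the third.

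- **Entry.** The gap to the second attack is analysed "only for subjects experiencing at least one attack which ends within the Treatment Period". The gap to the third has the matching condition on the second attack.
- **Censoring.** "Subjects without a second attack will be censored at the EoT Visit date", and "Subjects without a third attack will be censored at the EoT Visit date". Protocol 9.4.2.2.1 agrees: "Subjects with no HAE attack, no second HAE attack, no third HAE attack, etc, will be censored at the End of Treatment Visit".
- **Quartiles.** The median and quartiles are "the times for which the Kaplan-Meier estimates for the time-to-event functions equal 0.5, 0.75, and 0.25, respectively".
- **Curves.** "Kaplan-Meier curves with two-sided 95% CI will be plotted showing the percentage of subjects being event-free at certain times".
- **Percentages for the two gaps.** Directly after the curve sentence and before the life tables: "the percentages will be calculated using the number of subjects not having the second/third attack at that time as the numerator", with "the number of subjects having at least one/two event(s) as the denominator".

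The protocol has no counterpart to the last rule.

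**The concern.** The last rule is a crude proportion with a fixed denominator and no risk set. A child whose first attack ends on Day 331 is followed for 30 days (361 − 331), yet the fraction still counts that child as free of a second attack at 90, 180 and 270 days. Such short follow-up is built into the design: each gap clock starts when the previous attack ends, while treatment ends for everyone at about Day 361.

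A programmer therefore has two incompatible instructions for one quantity. Following the literal one would give percentages free of the next attack that lean in the favourable direction, increasingly so at later times and more for the third attack. They would sit beside Kaplan-Meier quartiles and confidence bands that do not match them.

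**Working it through.** The plan states no figure for these percentages, so there is nothing to reproduce. The check compares the two rules.

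**1. Direction.** Let n children enter, let S be the Kaplan-Meier estimate, and let c be the censoring time of a child censored by time t.

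- Literal fraction: F(t) = [number still followed and attack-free beyond t + number censored by t] / n.
- Kaplan-Meier in its self-consistent form: S(t) = [number still followed and attack-free beyond t + sum over children censored by t of S(t)/S(c)] / n.

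Each ratio S(t)/S(c) is at most 1, so F(t) ≥ S(t). The two are equal only if no next attack falls between a censoring time and t. A check on 5,000 random censored data sets found no case of F below S.

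**2. Six-child example (invented data).** First attacks end on Days 40, 120, 200, 260, 300 and 340, with EoT on Day 361 (Protocol 1.3). Second attacks follow after 60 and 90 days in the first two children only. The other gaps are censored at 161, 101, 61 and 21 days.

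- Day 60: five at risk, one attack; S = 4/5 = 0.80, F = 5/6 = 0.83.
- Day 90: three at risk, one attack; S = 0.80 × 2/3 = 0.53, F = 4/6 = 0.67.
- Cross-check by the formula in step 1, just after day 90: (2 + 0.533/1 + 0.533/0.80)/6 = 3.2/6 = 0.53.

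The contrast of 67% with 53% holds from day 90 to day 161. After that no child is under observation.

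**3. Expected size.** Assumptions: mean rates of 0.05 to 0.35 attacks per month, constant or gamma-varying between children; 3-day attacks; 361 days. The two rates are the means of the 200 mg and 600 mg arms of the phase 2 study (Protocol 2.1.1.2.2), used only as a range. The documents give no on-treatment rate for children. With 400,000 simulated children per scenario, the excess of F over S was:

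| Gap time | Second attack | Third attack |
|---|---|---|
| 180 days | about 2 to 7 points | about 7 to 14 points |
| 270 days | about 4 to 13 points | about 11 to 24 points |

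**4. At the planned size.** Averages over simulated trials of 20 children, constant rate, 360 days, at 180 days of the gap. The last column is children entering × excess.

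| Rate per month | Next attack | Children entering | Kaplan-Meier | Fraction | Excess (points) | In children |
|---|---|---|---|---|---|---|
| 0.1 | second | 13.7 | 55.1% | 61.3% | 6.2 | 0.8 |
| 0.1 | third | 6.5 | 59.1% | 69.9% | 10.8 | 0.7 |
| 0.2 | second | 18.2 | 31.0% | 36.1% | 5.1 | 0.9 |
| 0.2 | third | 13.5 | 32.2% | 45.0% | 12.8 | 1.7 |
| 0.5 | third | 19.6 | 5.2% | 7.9% | 2.7 | 0.5 |

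At 1.0 per month with a constant rate there is no visible difference, because almost no gap is censored.

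**5. Denominator.** The fraction counts every child with at least one (two) attacks, whereas entry requires that attack to have ended within the Treatment Period. A seventh child whose first attack is still ongoing at EoT would enter the fraction, as attack-free, but not the Kaplan-Meier analysis: (4 + 1)/(6 + 1) = 71%.

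**The case against.** A reader might infer that the SAP has decided to plot biased curves. The documents do not support that. The same section specifies Kaplan-Meier curves with confidence intervals and Kaplan-Meier quartiles, and censored observations are flagged in the listing. Anything produced that way is unaffected.

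The sentence could also be meant more narrowly. It may only fix the base (children who had the earlier attack, not all enrolled children), or it may belong to the earlier bullet counting subjects without the event, where a simple proportion is ordinary. The table shells are a separate document and might settle this. The narrower reading cannot be excluded, but it fits the text poorly. A choice of base needs no numerator, and none tied to a time. The bullet has no time point, while the sentence just before does. The base is also already fixed by the entry rule, in different terms.

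The wording even allows a third reading. If the numerator meant children still under observation without the attack, the example would give 2/6 = 33% just after day 90, below Kaplan-Meier. That adds to the case for clarifying the text.

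The remaining objection is scale, and it stands. These are supplementary summaries, and neither document plans any test or comparison (Protocol 9.4.6, SAP 9.4). At 0.05 attacks per month only about 2 to 3 of 20 children would enter the third-attack analysis; across the assumed range it is about 2 to 18.

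**Conclusion.** The point holds as an internal contradiction in SAP 9.2.1.5, with a conditional consequence: if the fraction is programmed as written, the percentages free of a second or third attack equal or exceed the Kaplan-Meier values. The direction is certain under the literal reading. The size rests on assumed attack rates and, at the planned sample size, is often about one child or less. It is largest at low rates, where many gaps are censored.

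Kaplan-Meier removes the contradiction but is not free of bias here. When rates differ between children, censoring of gap times is not independent. In the simulations of step 3 it stayed within about 3 points of the true gap distribution. The primary safety and PK endpoints and the named secondary efficacy endpoints do not use these percentages. This should be corrected, but it does not threaten the study's conclusions.

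**What to change.** Replace the numerator-and-denominator sentence in SAP 9.2.1.5 with:

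> For the second (third) attack, the time-specific percentages in the curves and life tables are Kaplan-Meier estimates among subjects whose first (second) attack ended within the Treatment Period, with numbers at risk shown.

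Keep the simple count and percentage only for the bullet on subjects who do not have the event during the Treatment Period, and give it the same base. Align the table and figure shells.

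The cost is one SAP sentence and the matching shells, with no new data. The only downside is that the reported percentages become slightly less favourable than the literal fraction would make them.
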